8.3 ADVERSE EVENTS AND SERIOUS ADVERSE EVENTS

8.3.1 DEFINITION OF ADVERSE EVENTS

An **adverse event** (AE) is any symptom, sign, illness, or experience that develops or worsens in severity during the study. Intercurrent illnesses or injuries should be regarded as adverse events. Abnormal results of diagnostic procedures are adverse events if the abnormality:

- results in study withdrawal
- is associated with a serious adverse event
- is associated with clinical signs or symptoms
- leads to additional treatment or to further diagnostic tests
- is considered by the investigator to be of clinical significance

8.3.2 DEFINITION OF SERIOUS ADVERSE EVENTS

Adverse events are classified as serious or non-serious. A **serious adverse event** is any AE that is:

- fatal
- life-threatening
- requires or prolongs hospital stay
- results in persistent or significant disability or incapacity
- a congenital anomaly or birth defect
- an important medical event

Important medical events are those that may not be immediately life threatening but are clearly of major clinical significance. They may jeopardize the subject and may require intervention to prevent one of the other serious outcomes noted above. For example, drug overdose or abuse, a seizure that did not result in in-patient hospitalization, or intensive treatment of bronchospasm in an emergency department would typically be considered serious.

All adverse events that do not meet any of the criteria for serious should be regarded as **non-serious adverse events**.

8.3.3 CLASSIFICATION OF AN ADVERSE EVENT

8.3.3.1 SEVERITY OF EVENT

Severity will be determined from the grades presented in National Cancer Institute (USA) Common Terminology Criteria for Adverse Effects version 4.0 (published August 9, 2006) (CTCAE v4.0) guidelines. The CTCAE v4.0 displays Grades 1 through 5 with unique clinical descriptions of severity for each AE based on this general guideline:

- Grade 1 – Mild AE
- Grade 2 – Moderate AE
- Grade 3 – Severe AE
- Grade 4 – Life-threatening or disabling AE
- Grade 5 – Death related to AE

All adverse events will be monitored until they are adequately resolved or explained

8.3.3.2 RELATIONSHIP TO STUDY INTERVENTION/EXPERIMENTAL MANIPULATION

Each adverse event will be judged by the Investigator as to its relationship and level of relatedness to the investigational device. Relatedness will be scored consistent with CTCAE v4.0 guidelines:

- Unrelated – the AE is clearly not related to the investigational agent(s),
- Unlikely – the AE is doubtfully related to the investigational agent(s),
- Possible – the AE may be related to the investigational agent(s),
- Probable – the AE is likely related to the investigational agent(s),
- Definite – the AE is clearly related to the investigational agent(s).

8.3.3.3 EXPECTEDNESS

The principal investigators will be responsible for determining whether an AE is expected or unexpected. An AE will be considered unexpected if the nature, severity, or frequency of the event is not consistent with the risk information previously described in this protocol for the study agent.

8.3.4 TIME PERIOD AND FREQUENCY FOR EVENT ASSESSMENT AND FOLLOW-UP

The occurrence of an AE or SAE may come to the attention of study personnel during study visits and interviews of a study participant presenting for medical care, or during the bi-monthly check-ins. All AEs including local and systemic reactions not meeting the criteria for SAEs will be logged. Information to be collected includes event description, time of onset, clinician's assessment of severity, relationship to study product (assessed only by those with the training and authority to make a diagnosis), and time of resolution/stabilization of the event. All AEs occurring while on study must be documented appropriately regardless of relationship. All AEs will be followed to adequate resolution.

Any medical condition that is present at the time that the participant is screened will be considered as baseline and not reported as an AE. However, if the study participant's condition deteriorates at any time during the study, it will be recorded as an AE. Unexpected problems (UPs) will be recorded in the data collection system throughout the study.

Changes in the severity of an AE will be documented to allow an assessment of the duration of the event at each level of severity to be performed. AEs characterized as intermittent require documentation of onset and duration of each episode.

The PI will record all reportable events with start dates occurring any time after informed consent is obtained until 7 (for non-serious AEs) or 30 days (for SAEs) after the last day of study participation. At each study visit, and at the bi-monthly check-ins, the investigator will inquire about the occurrence of AE/SAEs since the last visit. Events will be followed for outcome information until resolution or stabilization.

All unresolved adverse events should be followed by the investigator until the events are resolved, the subject is lost to follow-up, or the adverse event is otherwise explained. At the last scheduled visit, the investigator should instruct each subject to report any subsequent event(s) that the subject, or the subject's personal physician, believes might reasonably be related to participation in this study. The investigator should notify the study sponsor of any death or adverse event occurring at any time after a subject has discontinued or terminated study participation that may reasonably be related to this study. The sponsor should also be notified if the investigator should become aware of the development of cancer or of a congenital anomaly in a subsequently conceived offspring of a subject that has participated in this study.

8.3.5 ADVERSE EVENT REPORTING

AEs that are unanticipated, determined to be at least “probably related” to the study intervention, and reveal a “greater risk of harm” than originally expected will be considered reportable new information and reported within 5 business days of the principle investigator(s) becoming aware of the event.

Reports, signed by a principle investigator, will include the following information:

- Protocol identifying information: protocol title and number, PI’s name, and the IRB project number;
- A detailed description of the event, incident, experience, or outcome;
- An explanation of the basis for determining that the event, incident, experience, or outcome is unanticipated, at least probably related to the study intervention, and reveals a “greater risk of harm” than originally expected;
- A description of any changes to the protocol or other corrective actions that have been taken or are proposed in response to the unanticipated adverse events.

All other adverse events will be reported annually to the IRB.

Note that the period of trial participation is defined as occurring between randomization and close of the last visit window as defined by the protocol. Therefore, only AEs occurring after randomization and before the close of the last visit window will be logged. UPs that are not AEs will be noted separately between time of trial enrollment and study completion.

8.3.6 SERIOUS ADVERSE EVENT REPORTING

All SAEs will be reported to the IRB as soon as possible and certainly within 5 business days of the principle investigator(s) becoming aware of the event.

Reports, signed by a principle investigator, will include the following information:

- Protocol identifying information: protocol title and number, PI’s name, and the IRB project number;
- A detailed description of the event, incident, experience, or outcome;
- An explanation of the basis for determining that the event, incident, experience, or outcome represents a serious adverse event;
- A description of any changes to the protocol or other corrective actions that have been taken or are proposed in response to the serious adverse event.

8.4 UNANTICIPATED PROBLEMS

8.4.1 DEFINITION OF UNANTICIPATED PROBLEMS

Any incident, experience, or outcome that meets all of the following criteria:

- Unexpected in nature, severity, or frequency (i.e., not described in study-related documents such as the IRB-approved protocol or consent form, the investigators brochure, etc.)
- Related or possibly related to participation in the research (i.e., possibly related means there is a reasonable possibility that the incident experience, or outcome may have been caused by the procedures involved in the research)

- Suggests that the research places subjects or others at greater risk of harm (including physical, psychological, economic, or social harm).

This definition could include an unanticipated adverse device effect, any serious adverse effect on health or safety or any life-threatening problem or death caused by, or associated with, a device, if that effect, problem, or death was not previously identified in nature, severity, or degree of incidence in the investigational plan or application (including a supplementary plan or application), or any other unanticipated serious problem associated with a device that relates to the rights, safety, or welfare of subjects (21 CFR 812.3(s)).

8.4.2 UNANTICIPATED PROBLEMS REPORTING

Unanticipated problems that are determined to be at least “probably related” to the study intervention, and reveal a “greater risk of harm” than originally expected will be considered reportable new information and reported within 5 business days of the principle investigator(s) becoming aware of problem. Other unanticipated problems will be reported within 10 business days of the principle investigator(s) becoming aware of the problem.

Reports, signed by a principle investigator, will include the following information:

- Protocol identifying information: protocol title and number, PI’s name, and the IRB project number;
- A detailed description of the event, incident, experience, or outcome;
- An explanation of the basis for determining that the event, incident, experience, or outcome is unanticipated, at least probably related to the study intervention, and reveals a “greater risk of harm” than originally expected;
- A description of any changes to the protocol or other corrective actions that have been taken or are proposed in response to the unanticipated problem.

9 STATISTICAL CONSIDERATIONS

9.1 STATISTICAL HYPOTHESES

- Primary Endpoint:

We hypothesize home transcranial photobiomodulation (tPBM) treatments delivered with the NeuroGamma device will be safe and that patients with mild-to-moderate AD will find home tPBM treatments tolerable.

- Secondary Endpoint(s):

We hypothesize that AD patients randomized to active tPBM have improved cognitive function (i.e., performance on the ADAS-cog, and CTT) and behavioral symptoms (i.e., NPI and ADCS-ADL) after 16 weeks compared to patients in the Sham group.

We hypothesize that AD patients randomized to active tPBM have decreased levels of NfL after 16 weeks compared to patients in the Sham group.

In exploratory analyses, we will examine the effects of 16 weeks of PBM on fluid levels of A β 42 and A β 42/A β 40, total- and p-tau. We will also explore the relationship between changes in cognition and behavior with changes in fluid biomarkers.

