1 PROTOCOL SUMMARY

1.1 SYNOPSIS

Title:	Examining the Impact of Photobiomodulation on Cognition, Behavior, and Biomarkers of Alzheimer’s Disease.
Study Description:	The proposed sham-controlled pilot trial will investigate the safety and tolerability of 16 weeks of home transcranial photobiomodulation (tPBM) treatment with commercially available device (i.e., Vielight Neuro Gamma) in 14 patients with mild-to-moderate Alzheimer’s Disease (AD). We will also examine the effects of home PBM on the cognitive function, behavioral symptoms, cerebrospinal fluid and blood biomarkers of AD pathology, including amyloid burden, tangle pathology, axonal injury, microglia activation/inflammation, and neurotrophic factors. We hypothesize that home PBM treatments will be safe and tolerable. We further hypothesize that effect sizes will suggest AD patients randomized to the active PBM condition have improved cognitive function and fewer behavioral symptoms after 16 weeks compared to patients randomized to Sham. Based on reports that PBM upregulates neuroprotective factors, reduces neuroinflammation, induces peripheral and central nerve regeneration, and prevents degeneration, we hypothesize that these behavioral improvements will correlate with changes in fluid biomarkers of neurodegeneration (i.e., neurofilament light chain, NfL) and Alzheimer’s disease (e.g., A β 42 and A β 42/A β 40, total- and phosphorylated-tau).
Objectives:	Primary Objective: Examine the safety and tolerability of home tPBM delivered with a commercially available PBM device. Secondary Objectives: Examine the effects of home tPBM on cognition, behavior, and fluid biomarkers of AD.
Endpoints:	Primary: All adverse events Secondary: Change in ADAS-cog and biochemical biomarkers (A β 40, A β 42, total and phosphorylated tau, NfL)
Study Population:	Men and women, ages 50 years or older with have prodromal, mild or moderate typical or atypical AD, supported by clinical AD biomarkers and a Mini-Metal State Exam (MMSE) score > 13.
Phase or Stage:	1B
Description of Sites/Facilities Enrolling Participants:	San Francisco VA Medical Center and University of California Memory and Aging Center
Description of Study Intervention/Experimental Manipulation:	Transcranial and intranasal photobiomodulation, delivers near-infrared light ($\lambda = 810 \text{ nm}$, 40 Hz, 40-150 mW/cm ²) to the scalp and one nostril.
Study Duration:	36 months
Participant Duration:	4-8 months

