3 OBJECTIVES AND ENDPOINTS

The primary objective of the study is to assess the safety and tolerability of home transcranial photobiomodulation (tPBM) treatments delivered with a commercially available PBM device (i.e., the Vielight Neuro Gamma device). The primary endpoint will be all adverse events.

The secondary objects of the study are to examine the effects of home tPBM on cognition, behavior, and fluid biomarkers of AD in patients with biomarker confirmed diagnoses of mild-to-moderate AD. Secondary endpoints will be change in the Alzheimer's Disease Assessment Scale, Cognitive Subscale (ADAS-cog), and change in fluid biomarkers of AD (e.g., A β 40, A β 42, total and phosphorylated tau, neurofilament light chain).

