9.2 SAMPLE SIZE DETERMINATION

The purpose of the proposed study is to gather the data required so that effect size estimates may be calculated for each of the study hypotheses. Moreover, there are no published human studies on the effects of tPBM on levels of these biomarkers. Therefore, one of the goals of this study is to obtain a reliable effect size estimate of tPBM on brain function and fluid biomarkers of neurodegeneration, inflammation, and neurotropic factors in anticipation of a larger PBM dementia trial. Power analyses suggest that based on our proposed sample size (8 randomly assigned to tPBM and 8 to sham), at power = .80 and alpha = .05, we will be able to detect evidence of meaningful between-group differences (≥ 0.25 SDs) in the behavioral and biomarker outcome measures.

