9.3.2 ANALYSIS OF THE PRIMARY ENDPOINT(S)

Safety and AEs will be assessed at each in-person study visit and during bi-monthly check-ins. We will use Kolmogorov-Smirnov test to compare the number of AEs in each group. To examine tolerability, we will determine the total number of treatment days and average treatment days per week in each group.

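### The primary hypothesis is that home tPBM is safe and tolerable, but the only primary test is of equal AE counts, so a non-significant result cannot support it

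*Combined protocol and SAP*

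**What the plan says.** Section 3 makes safety and tolerability the primary objective and adds: "The primary endpoint will be all adverse events". Section 9.1 turns the objective into an assertion, that home tPBM "treatments delivered with the NeuroGamma device will be safe and that patients with mild-to-moderate AD will find home tPBM treatments tolerable".

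Section 9.3.2 holds the whole primary analysis. Apart from saying when AEs are assessed, it has two sentences. On safety: "We will use Kolmogorov-Smirnov test to compare the number of AEs in each group". On tolerability: "To examine tolerability, we will determine the total number of treatment days and average treatment days per week in each group".

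Section 9.2 gives a power statement for a sample of "8 randomly assigned to tPBM and 8 to sham), at power = .80 and alpha = .05", but only for "meaningful between-group differences (≥ 0.25 SDs) in the behavioral and biomarker outcome measures". The Synopsis describes a trial "in 14 patients with mild-to-moderate" AD, which is 7 per arm at 1:1 allocation.

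No section gives a margin, a confidence interval, a maximum event rate or a minimum adherence by which safe or tolerable could be judged. Interim analyses are marked as not applicable (9.3.5), and termination for safety reasons has no numerical trigger (section 7).

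**The concern.** The hypothesis and its test point in opposite directions. The hypothesis asserts that the treatment is safe. The test assumes equal AE distributions and looks for evidence against that. Failing to find such evidence with 7 or 8 patients per arm says little, because the result is compatible with equality and with a substantial excess. A different test of difference would have the same null, so the choice of Kolmogorov-Smirnov is not the root of the problem.

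The tolerability half has no inference at all: treatment days are tabulated, without an interval or a reference value.

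Section 9.2 says the data are meant to prepare a larger trial. If the report says that AEs did not differ significantly, that trial could inherit a safety statement the data do not carry. The documents make an excess conceivable: section 2.2.1 cites a 16-session study with more mild side effects under active treatment.

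**Working it through.** **The plan's own figure.** No power or precision is stated for AEs. The only figure is 80% power at 0.25 SD for the behavioral and biomarker outcomes. It does not reproduce: with 8 per arm the noncentrality is 0.25 × √(8/2) = 0.5, and a two-sided t test at 0.05 has power 7.5%. Reaching 80% needs n = 2(1.960 + 0.842)²/0.25² ≈ 252 per arm. That is a separate defect. Here it matters only that the statement does not cover the primary endpoint.

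**Inputs.** 8 per arm (9.2) or 7 per arm (Synopsis); two-sided alpha 0.05 (sidedness is not stated, so two-sided is assumed). The AE rate is not in the documents, so sham means of 0.5 to 8 AEs per patient are assumed, with the active mean doubled.

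**Rejection rule.** For the exact two-sample Kolmogorov-Smirnov test:
- 8 per arm: D = 5/8 gives p = 0.087 and D = 6/8 gives p = 0.019, so D must be at least 6/8.
- 7 per arm: D = 5/7 gives p = 0.053 and D = 6/7 gives p = 0.008, so D must be at least 6/7.

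Because AE counts are tied, the real type I error with 8 per arm is only about 0.2% to 1.3%.

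**Chance of a non-significant result when active AEs truly double** (simulated; separate runs differ by about one percentage point):

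| Sham v active mean | Poisson, 8 per arm | Poisson, 7 per arm | Overdispersed*, 8 per arm |
|---|---|---|---|
| 0.5 v 1 | 97% | 99% | 98% |
| 1 v 2 | 93% | 97% | 96% |
| 2 v 4 | 80% | 90% | 93% |
| 3 v 6 | 64% | 80% | 91% |
| 5 v 10 | 36% | 58% | 88% |
| 8 v 16 | 12% | 30% | 86% |

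*Negative binomial, dispersion 0.5. With dispersion 1 the range is 93% to 99%.

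**How much is the test and how much the sample.** With Poisson counts and 8 per arm, a rank-sum test is non-significant about 71% of the time at 1 v 2 and 46% at 2 v 4, against 93% and 80% above. So a good part of the figures reflects Kolmogorov-Smirnov. What remains comes from the sample size.

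**What the data could exclude, whichever test is used.**
- Suppose the observed AE rates are equal. The upper 95% limit of the rate ratio is then exp(1.96 × √(2/(n × mean))). With n = 8 this is exp(1.96 × 0.5) = 2.7 at a mean of 1, exp(1.96 × 0.354) = 2.0 at a mean of 2, and exp(1.96 × 0.224) = 1.6 at a mean of 5.
- Zero of 8 active patients with a given event excludes only true rates above 1 − 0.05^(1/8) = 31% (one-sided 95%). Zero of 7 excludes only rates above 1 − 0.05^(1/7) = 35%.
- An event with true incidence 20% is not seen at all in 8 active patients with probability 0.8^8 = 17%.

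**The case against.** **No decision rule is stated.** A reader might infer that the plan will declare tPBM safe if the AE comparison is non-significant. No sentence says so, and the objectives are worded as examining and assessing safety in a phase 1B pilot. This stands. The point is that the stated analysis cannot support the stated hypothesis, not that a wrong conclusion has been announced.

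**The hypothesis can receive unfavorable evidence.** A reader might also infer that no likely result could count against it. The documents do not support that. A significant AE excess would count against safety, and few treatment days would count against tolerability. Events are graded and scored for relatedness (8.3.3) and reviewed individually and monthly in aggregate (10.1.4), and the study can be stopped for safety (section 7). None of this supplies a criterion or an interval, but it is not nothing.

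**AE counts may be high.** The AE definition in 8.3.1 is broad, staff ask twice a month (8.2), and there are two lumbar punctures. At 5 or more Poisson AEs per sham patient with 8 per arm, the planned test would more often than not detect a doubling. This also stands, and is why the whole range is shown. Overdispersion, 7 per arm, and the absence of AEs in the earlier study with this device (2.2.1) point the other way.

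**Section 9.2 is not only about secondary outcomes.** It opens with an aim of estimating effect sizes for every study hypothesis; only the power sentence is limited to "in the behavioral and biomarker outcome measures". Correct, and that aim favors estimation for the primary endpoint as well.

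**Pass/fail thresholds in a pilot of 14 to 16 patients are partly a matter of preference.** Agreed. Criteria based on serious or severe events would also move the primary conclusion away from all adverse events. They are therefore not part of the main recommendation.

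**Conclusion.** The concern holds in this form: section 9.1 asserts safety and tolerability, section 9.3.2 tests only equality of AE counts and describes treatment days, and section 9.2 states no precision for either. A non-significant comparison cannot support the assertion. That conclusion follows from the text and does not depend on any AE rate.

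How likely such an uninformative result is does depend on the AE rate, which the documents do not give. For a true doubling with Poisson counts, it runs from about 97% at 0.5 AEs per sham patient to about 12% at 8 with 8 per arm, and from about 99% to 30% with 7 per arm. With overdispersed counts and 8 per arm it is at least 86% throughout. Part of this is the choice of test. The exclusion limits of 31% and 35% rest only on the number of active patients. This should be changed, and wording is enough.

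**What to change.** - **9.3.2, safety.** Make the primary analysis estimation. Report per arm the number and proportion of patients with any AE, any device-related AE, any Grade 3 or higher AE and any SAE, each with an exact 95% confidence interval, and the between-arm difference or rate ratio with its interval. All adverse events remain the endpoint.
- **9.3.2, tolerability.** Report treatment days and the proportion of scheduled sessions completed, with an interval. The denominator must first be settled. Section 4.1 and Table 1 give three sessions per week (3 × 16 = 48), while 6.1.2 also allows every other day (112/2 = 56 over 16 weeks). The sponsor must reconcile these passages.
- **9.2.** State what the sample can exclude: with zero events, only true rates above 31% for 8 active patients or 35% for 7 (one-sided 95%).
- **9.1, and the matching hypothesis in the Synopsis.** Restate the aim as estimating preliminary safety and tolerability, and say that a non-significant AE comparison will not be reported as evidence of safety.
- **Optional.** Numerical criteria for safe or tolerable are for the sponsor to choose. They would have to be fixed before enrollment, because AEs are reviewed in real time (10.1.4).

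The cost is wording only, with no extra patients, visits or data. The downside is a more modest claim: preliminary safety rather than safe.
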